2.4 OTT166 Background

DR is caused by damage to retinal blood vessels in patients with diabetes and is the leading cause of blindness among the United States working-age population. The disease starts with the formation of microaneurysms and progresses to hemorrhages and neovascularization of the retina and vitreous. At any point along this continuum, vessels can leak fluid into the macula, causing diabetic macular edema (DME) and consequently cause loss of eyesight, particularly if the fluid accumulates in the center of the macula. Patients with mild or moderate DR have an approximately 23% chance of progressing to severe disease over 5 years and an approximately 60% chance of developing DME ([Cheung 2010](#), [Ferris 1987](#), [Wang 2018](#)).

Integrins are proteins found on the surface of cells that help them attach to, and communicate with nearby cells, and play an important role in cell growth, cell movement, and other cell functions. Integrins are comprised of an α subunit and a β subunit and 24 $\alpha\beta$ combinations have been identified. Integrins that recognize ligands with an RGD sequence, called RGD-binding integrins, play key roles in the 4 hallmarks of DR: vascular leakage, neovascularization, inflammation, and fibrosis ([Figure 1](#)). Expression of high levels of the integrin $\alpha_v\beta_3$ and $\alpha_v\beta_5$ in human retinal membranes from patients with proliferative DR have been reported.

Figure 1 RGD-Binding Integrins Involved in the Pathogenesis of Diabetic Retinopathy

RGD = arginine-glycine-aspartic acid.

Source: Van Hove I, Hu TT, Beets K, et al. Targeting RGD-binding integrins as an integrative therapy for diabetic retinopathy and neovascular age-related macular degeneration. *Prog Retin Eye Res.* 2021;85:100966.

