2.8 Inclusion Criteria

Participants are eligible to be included in the study only if all the following criteria apply:

1. Men or women ≥ 18 years of age with type 1 or 2 diabetes mellitus who have moderately severe to severe NPDR [DRSS levels 47 or 53], or mild PDR [DRSS level 61B] NVE < 0.5 DA in 1 + quadrants], in whom PRP and/or anti-VEGF IVT can be safely deferred for at least 6 months per the Investigator ([ETDRS report 1991](#)).
2. BCVA ETDRS letter score in the study eye of ≥ 69 letters (approximate Snellen equivalent of 20/40 or better)
3. Normal foveal contour
4. Treatment naïve (ie, no previous anti-VEGF or steroid treatment or PRP or laser)
5. Willing and able to return for all study visits and comply with study-related procedures
6. Able to adhere to the study dosing requirements
7. Understands and signs the written ICF

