2.16.5 Optical Coherence Tomography (OCT)

Structural OCT (widefield preferred) will be performed by using spectral domain devices. The specific device models accepted for the study will be defined by the central reading center. OCTs will be performed at every visit by qualified technicians following an acquisition protocol of the central reading center. OCTs will also be used for local safety assessment. Newly found clinically significant pathologies should be reported as AEs. All obtained images will be sent to the central reading center for evaluation, and central reading center data will be used for the final analysis.

At screening, a standardized set of OCT images will be sent to the central reading center for evaluation and eligibility assessment. Beside central subfield thickness within the central 1 mm (CST) and whole macular volume also the presence of center involving and non-center involving macular edema will be assessed. SD-OCT will be also assessed for foveal contour and several exploratory outcome parameters and morphologic predictive biomarkers.

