2.16.6 Optical Coherence Tomography Angiography (OCTA)

OCTA is optional at sites that have an OCTA. The OCTA needs to be performed by a qualified technician following an acquisition protocol of the central reading center at Visits 1 and 8, as scheduled in the SoA (Section 2.15.1). The specifications of this OCTA can be found in the acquisition protocol of the central reading center. Images obtained via OCTA will be sent to the Central Reading Center for evaluation. Several quantitative and qualitative parameters, including the FAZ and area of nonperfusion, which have been shown to be associated with DR severity, will be assessed.

2.16.7 *Slit Lamp Biomicroscopy (Anterior and Posterior Segment)*

The slit lamp examination (anterior and posterior segment) will be performed according to local medical practice and applicable medical standards at the site at every visit, as stated in the SoA ([Section 2.15.1](#)). Abnormal findings are to be recorded in the eCRF as either medical history or AE, as applicable.

2.16.8 *Tonometry (Intraocular Pressure (IOP) Measurement)*

IOP is to be measured at every visit with any locally approved non-contact tonometer.

If there is no non-contact tonometer available at the site, applanation tonometry (Goldmann, Tonopen, or other locally approved alternatives) may be used. In any case, where both methods are available, the non-contact method is to be used. In cases in which Goldmann applanation tonometry (GAT) is used, assessment of corneal health using fluorescein stain should be performed prior to tonometer applanation.

The same method of IOP measurement must be used throughout the study for each individual participant and should be performed at approximately the same time of day, if possible. Values, including time of day and measuring type, are to be recorded in the eCRF.

2.16.9 *Vision-threatening Complications*

VTC is defined as the composite outcome of PDR (inclusive of participants who have vitreous hemorrhage or tractional retinal detachment believed to be due to PDR) and/or ASNV identified by Investigators (participants with neovascularization of the iris [at least 2 cumulative clock hours], and/or definitive neovascularization of the iridocorneal angle) and/or CI-DME as defined in [Section 2.16.10](#) below.

VTCs are defined as occurrence of any of the following AEs:

- More than mild PDR (DRSS 65 and above)
- Iris neo-vascularization
- CI-DME

2.16.10 *DME and CI-DME*

DME is defined as fluid in the macula.

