CI-DME is defined as the presence of fluid in the central subfield in participants who have no fluid at baseline or CST > 325 μm .

The assessment will be continued after treatment discontinuation until end of study.

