3.4.2 Events Meeting the AE Definition

- Any abnormal laboratory test results (hematology, clinical chemistry, or urinalysis) or other safety assessments (eg, radiological scans, vital signs measurements), including those that worsen from BL, considered clinically significant in the medical and scientific judgment of the Investigator (ie, not related to progression of underlying disease).
- Exacerbation of a chronic or intermittent pre-existing condition including either an increase in frequency and/or intensity of the condition.
- This includes progression of DR New conditions detected or diagnosed after study intervention administration even though it may have been present before the start of the study.
- Signs, symptoms, or the clinical sequelae of a suspected intervention-intervention interaction.
- Signs, symptoms, or the clinical sequelae of a suspected overdose of either study intervention or a concomitant medication. Overdose per se will not be reported as an AE/SAE unless it is an intentional overdose taken with possible suicidal/self-harming intent. Such overdoses should be reported regardless of sequelae.

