3.4.3 Events NOT Meeting the AE Definition

- Any clinically significant abnormal laboratory findings or other abnormal safety assessments which are associated with the underlying disease, unless judged by the Investigator to be more severe than expected for the participant's condition.
- The disease/disorder being studied or expected progression, signs, or symptoms of the disease/disorder being studied, unless more severe than expected for the participant's condition.
- Medical or surgical procedure (eg, endoscopy, appendectomy): the condition that leads to the procedure is the AE.

- Situations in which an untoward medical occurrence did not occur (social and/or convenience admission to a hospital).
- Anticipated day-to-day fluctuations of pre-existing disease(s) or condition(s) present or detected at the start of the study that do not worsen.

An SAE is defined as any AE that, at any dose:

a. Results in death

b. Is life-threatening

- The term 'life-threatening' in the definition of 'serious' refers to an event in which the participant was at risk of death at the time of the event. It does not refer to an event, which hypothetically might have caused death, if it were more severe.

c. Requires inpatient hospitalization or prolongation of existing hospitalization

- In general, hospitalization signifies that the participant has been admitted (usually involving at least an overnight stay) at the hospital or emergency ward for observation and/or treatment that would not have been appropriate in the physician's office or outpatient setting. Complications that occur during hospitalization are AEs. If a complication prolongs hospitalization or fulfills any other serious criteria, the event is serious. When in doubt as to whether "hospitalization" occurred or was necessary, the AE should be considered serious.
- Hospitalization for elective treatment of a pre-existing condition that did not worsen from BL is not considered an AE.

d. Results in persistent or significant disability/incapacity

- The term disability means a substantial disruption of a person's ability to conduct normal life functions.
- This definition is not intended to include experiences of relatively minor medical significance such as uncomplicated headache, nausea, vomiting, diarrhea, influenza, and accidental trauma (eg, sprained ankle) which may interfere with or prevent everyday life functions but do not constitute a substantial disruption.

e. Is a congenital anomaly/birth defect

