**3.2 Endpoints**

**3.2.1 Primary Endpoint - Safety**

The primary safety outcome measure of the study will be the proportion of participants who develop TEAEs through Week 24.

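### Protocol 3.4.2 and 3.4.3 disagree on whether progression of diabetic retinopathy is an adverse event, and the SAP does not say whether such events count in the primary safety proportion

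*Protocol*

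**What the plan says.** SAP 3.2.1 sets the endpoint: "The primary safety outcome measure of the study will be the proportion of participants who develop TEAEs through Week 24". Protocol 2.20.2 has the same measure.

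What counts as an AE is left to Protocol Appendix 4, where two sections bear on diabetic retinopathy (DR):

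- Section 3.4.2 (events that are AEs) lists exacerbation of a pre-existing condition and then states "This includes progression of DR". There is no severity condition. The bullet runs straight into the next item, so where it ends is unclear.
- Section 3.4.3 (events that are not AEs) lists "The disease/disorder being studied or expected progression, signs, or symptoms of the disease/disorder being studied, unless more severe than expected". The protocol does not say what degree of progression is expected.

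Two other places touch the same events. Section 2.16.9 introduces more than mild PDR (DRSS 65 and above), iris neovascularization and CI-DME with "VTCs are defined as occurrence of any of the following AEs". Section 2.16.5, on OCT findings, says "Newly found clinically significant pathologies should be reported as AEs".

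SAP 4.11.1 defines a TEAE by onset at or after dosing on Day 1, counts a participant once per preferred term and system organ class, and gives rules for missing start dates and missing causality. It does not mention progression of DR.

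The definition of a TEAE also varies. Protocol 2.18.1 adds pre-dose AEs that worsen after dosing, whereas Protocol 2.21.5 and SAP 4.11.1 use onset alone.

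**The concern.** Every participant has DR at entry, and the study eye is photographed at every visit, so worsening is actively looked for. If one site treats a step of worsening as an AE and another treats it as the expected course of the disease, the same event enters the primary safety proportion at one site and not at the other.

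The disputed events are also efficacy outcomes. DRSS worsening by 1, 2 or at least 3 steps, worse than mild PDR, ASNV, CI-DME and the VTC composite are all secondary endpoints (Protocol 2.20.2, SAP 3.2.3). A proportion with any TEAE that includes some of them is partly a measure of disease progression, and a reader of the report cannot tell how large that part is.

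**Working it through.** The documents state no expected TEAE rate, so there is no figure to reproduce. The check is mainly a comparison of passages.

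**1. The same event under each section.**

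| Event | 3.4.2 | 3.4.3 | Elsewhere | Result |
|---|---|---|---|---|
| DR worsening short of a VTC, e.g. DRSS 47 to 53 | AE | Not an AE if of expected degree | Not addressed in 2.16.9 | Opposite answers |
| DRSS 65 and above, or iris neovascularization | AE | VTCs not exempted, but hard to call expected | 2.16.9 calls it an AE | Mostly an AE |
| CI-DME | AE if seen as progression of DR | Not an AE if expected | 2.16.9 calls it an AE; 2.16.5 requires clinical significance | Unclear |

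The middle row is less disputed because inclusion criterion 1 admits only participants "in whom PRP and/or anti-VEGF IVT can be safely deferred for at least 6 months per the Investigator". Follow-up is 24 weeks (24 × 7 = 168 days), which is shorter than 6 months, so reaching DRSS 65 in that time is hard to describe as expected.

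CI-DME is less clear. Section 2.16.10 says "CI-DME is defined as the presence of fluid in the central subfield in participants who have no fluid at baseline", or CST above 325 µm. That needs no loss of BCVA and no minimum change in CST, so it can occur without any objective rescue criterion being met. Section 2.4 describes DME as a common outcome of DR.

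**2. Does the severity clause in 3.4.3 reconcile the two?** No. It brings back progression that is worse than expected. Section 3.4.2 has no such limit, so progression of the expected degree is still in under one section and out under the other.

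**3. Does the SAP settle it?** SAP 4.14 lets the SAP supersede analyses planned in the protocol, but SAP 4.11.1 has no text on this point to do so. For AE definitions it points to Protocol Appendix 4, which holds both sections.

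**4. Do the planned tables show the effect?** Only in part. Let A be the number of participants in an arm with any TEAE, and D the number with a DR-progression or VTC term. The number with any other TEAE lies between A − D and A, because one participant can have several terms. Tables by eye, by relationship to drug and by preferred term do not say where in that interval it falls.

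**5. Size.** If r is the share of an arm with a disputed event, the two readings differ by the share whose only TEAEs are disputed events. That cannot exceed r. The documents give neither a 24-week r nor a rate of other TEAEs. The nearest figures are in Protocol 2.4, for mild or moderate DR: "approximately 23% chance of progressing to severe disease over 5 years and an approximately 60% chance of developing DME". Assuming a constant hazard, and that both figures cover 5 years (the text is not explicit for the second):

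- 24 weeks / 5 years = 24 / 260.9 = 0.0920
- 1 − (1 − 0.23)^0.0920 = 0.0238, about 2.4%
- 1 − (1 − 0.60)^0.0920 = 0.0808, about 8.1%

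These are not estimates of r. The enrolled eyes have more severe disease, the DME figure is not limited to CI-DME, and neither figure covers smaller DRSS steps.

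**6. Definition of a TEAE.** Protocol 2.18.1 and 2.21.5 differ on worsened pre-dose AEs. SAP 4.11.1 agrees with 2.21.5, and SAP 4.14 makes it govern the tables. What remains is a mismatch within the protocol.

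**The case against.** **A reconciling reading exists.** Section 3.4.3 is generic and 3.4.2 names DR. Letting the specific line prevail would make all DR progression an AE, in keeping with 2.16.9. This is possible, but no passage states it, and a site could as reasonably apply the exclusion. The eCRF completion guidelines mentioned in Protocol 3.1.6 were not available and may address it.

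**Sites may seldom face the conflict.** DRSS grading is done centrally, and the documents do not say that grades below 65 go back to sites. Investigators do examine the fundus and the photographs (2.16.2), so the question can arise. How often is unknown, and that is one reason why no size is given.

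**The data will be there anyway.** By-participant TEAE listings allow the count to be derived for recorded events, and the progression outcomes are reported by arm as efficacy endpoints. Both are true. A listing is still not a planned by-arm proportion, and this is a primary endpoint.

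**A reader might infer that the SAP has no counting rule at all.** It does have rules for timing, missing data and repeated events. The gap is limited to which DR events qualify.

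**A reader might also infer that one arm is favoured.** The documents do not support this. Masked sites applying either section would shift the level in all arms. Protocol 2.21.3 rules out inferential statistics on safety, so no alpha or power rests on the proportion.

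**Conclusion.** The point holds and is minor. Sections 3.4.2 and 3.4.3 contradict each other for DR progression short of a VTC and leave CI-DME uncertain. Section 2.16.9 covers the VTC components only in part, because 3.4.3 does not exempt them. SAP 4.11.1 does not settle whether these events count. As written, the primary safety proportion can depend on which section a site followed, and it can include disease progression already counted as efficacy.

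The documents do not allow the size to be estimated. It would be tempting to assume rates for progression and for other TEAEs and quote a range in percentage points, but those inputs would have no source in the protocol or SAP.

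The conclusion assumes that the words on DR progression in 3.4.2 are meant as they stand despite the run-on bullet, and that no unseen site guidance already resolves the conflict.

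**What to change.** 1. Reconcile Protocol 3.4.2, 3.4.3 and 2.16.9 into one recording rule. It should say, for study and fellow eyes, whether DR progression short of a VTC, and each VTC component, is an AE. Which way to decide is for the sponsor. Align the TEAE definition in 2.18.1 with 2.21.5 and SAP 4.11.1.

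2. Add to SAP 4.11.1:

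> The number and percentage of participants with any TEAE will be presented by treatment group (i) for all TEAEs and (ii) excluding DR-progression and VTC terms, in the study eye and in either eye. The term list will be fixed at the Data Review Meeting before unmasking.

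The fellow eye belongs in both items, because its DR events raise the same conflict and enter the same any-TEAE proportion.

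The cost is some rewording and one extra table, and SAP 4.4.1 already plans the meeting. There are limits. SAP 4.2 describes enrollment in the past tense, so item 1 may change little that has already been recorded. Item 2 can take recorded progression events out of the count, but it cannot restore events that sites never recorded.

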3.4.3 Events NOT Meeting the AE Definition

- Any clinically significant abnormal laboratory findings or other abnormal safety assessments which are associated with the underlying disease, unless judged by the Investigator to be more severe than expected for the participant's condition.
- The disease/disorder being studied or expected progression, signs, or symptoms of the disease/disorder being studied, unless more severe than expected for the participant's condition.
- Medical or surgical procedure (eg, endoscopy, appendectomy): the condition that leads to the procedure is the AE.

- Situations in which an untoward medical occurrence did not occur (social and/or convenience admission to a hospital).
- Anticipated day-to-day fluctuations of pre-existing disease(s) or condition(s) present or detected at the start of the study that do not worsen.

An SAE is defined as any AE that, at any dose:

a. Results in death

b. Is life-threatening

- The term 'life-threatening' in the definition of 'serious' refers to an event in which the participant was at risk of death at the time of the event. It does not refer to an event, which hypothetically might have caused death, if it were more severe.

c. Requires inpatient hospitalization or prolongation of existing hospitalization

- In general, hospitalization signifies that the participant has been admitted (usually involving at least an overnight stay) at the hospital or emergency ward for observation and/or treatment that would not have been appropriate in the physician's office or outpatient setting. Complications that occur during hospitalization are AEs. If a complication prolongs hospitalization or fulfills any other serious criteria, the event is serious. When in doubt as to whether "hospitalization" occurred or was necessary, the AE should be considered serious.
- Hospitalization for elective treatment of a pre-existing condition that did not worsen from BL is not considered an AE.

d. Results in persistent or significant disability/incapacity

- The term disability means a substantial disruption of a person's ability to conduct normal life functions.
- This definition is not intended to include experiences of relatively minor medical significance such as uncomplicated headache, nausea, vomiting, diarrhea, influenza, and accidental trauma (eg, sprained ankle) which may interfere with or prevent everyday life functions but do not constitute a substantial disruption.

e. Is a congenital anomaly/birth defect

f. Other situations:

- Medical or scientific judgment should be exercised by the Investigator in deciding whether SAE reporting is appropriate in other situations such as significant medical events that may jeopardize the participant or may require medical or surgical intervention to prevent one of the other outcomes listed in the above definition. These events should usually be considered serious.
- Examples of such events include invasive or malignant cancers, intensive treatment for allergic bronchospasm, blood dyscrasias, convulsions, or development of intervention dependency or intervention abuse.

3.4.4 *Recording and Follow-up of AE and / or SAE*

AE and SAE recording

- When an AE/SAE occurs, it is the responsibility of the Investigator to review all documentation (eg, hospital progress notes, laboratory reports, and diagnostics reports) related to the event.
- The Investigator will then record all relevant AE/SAE information.
- It is not acceptable for the Investigator to send photocopies of the participant's medical records to Sponsor in lieu of completion of the AE/SAE CRF page.
- There may be instances when copies of medical records for certain cases are requested by Sponsor. In this case, all participant identifiers, with the exception of the participant number, will be redacted on the copies of the medical records before submission to Sponsor.
- The Investigator will attempt to establish a diagnosis of the event based on signs, symptoms, and/or other clinical information. Whenever possible, the diagnosis (not the individual signs/symptoms) will be documented as the AE/SAE.

3.4.5 *Assessment of Intensity*

- The Investigator will make an assessment of intensity for each AE and SAE reported during the study and assign it to 1 of the following categories:
- Mild: An event that is easily tolerated by the participant, causing minimal discomfort and not interfering with everyday activities.
- Moderate: An event that causes sufficient discomfort to interfere with normal everyday activities.
- Severe: An event that prevents normal everyday activities. An AE that is assessed as severe should not be confused with an SAE. Severe is a category utilized for rating the intensity of an event; and both AEs and SAEs can be assessed as severe.
- An event is defined as 'serious' when it meets at least 1 of the predefined outcomes as described in the definition of an SAE, NOT when it is rated as severe.

3.4.6 *Assessment of Causality*

- The Investigator is obligated to assess the relationship between study intervention and each occurrence of each AE/SAE.
- A "reasonable possibility" of a relationship conveys that there are facts, evidence, and/or arguments to suggest a causal relationship, rather than a relationship cannot be ruled out.

- The Investigator will use clinical judgment to determine the relationship.
- Alternative causes, such as underlying disease(s), concomitant therapy, and other risk factors, as well as the temporal relationship of the event to study
- intervention administration will be considered and investigated.
- The Investigator will also consult the Investigator's Brochure (IB) and/or Product Information, for marketed products, in his/her assessment.
- For each AE/SAE, the Investigator **must** document in the medical notes that he/she has reviewed the AE/SAE and has provided an assessment of causality.
- There may be situations in which an SAE has occurred, and the Investigator has minimal information to include in the initial report to Sponsor. However, **it is very important that the Investigator always make an assessment of causality for every event before the initial transmission** of the SAE data to Sponsor.
- The Investigator may change his/her opinion of causality in light of follow-up information and send an SAE follow-up report with the updated causality assessment.
- The causality assessment is one of the criteria used when determining regulatory reporting requirements.

3.4.7 *Follow-up of AEs and SAEs*

- The Investigator is obligated to perform or arrange for the conduct of supplemental measurements and/or evaluations as medically indicated or as requested by Sponsor to elucidate the nature and/or causality of the AE or SAE as fully as possible. This may include additional laboratory tests or investigations, histopathological examinations, or consultation with other health care professionals.
- New or updated information will be recorded in the originally submitted documents.
- The Investigator will submit any updated SAE data to the Sponsor within 24 hours of receipt of the information.

3.4.8 *Reporting of SAEs*

SAE reporting to Sponsor via an electronic data collection tool

The primary mechanism for reporting an SAE to Sponsor will be the electronic data collection tool.

- If the electronic system is unavailable, then the site will use the paper SAE data transmission (see next section) to report the event within 24 hours.

- The site will enter the SAE data into the electronic system as soon as it becomes available.
- After the study is completed at a given site, the electronic data collection tool will be taken off-line to prevent the entry of new data or changes to existing data.
- If a site receives a report of a new SAE from a study participant or receives updated data on a previously reported SAE after the electronic data collection tool has been taken off-line, then the site can report this information on a paper SAE form (see next section) or to the Sponsor's Medical Monitor by telephone.
- Contacts for SAE reporting can be found in the Investigator Site File.

SAE reporting to Sponsor via paper data collection tool

- Email transmission of the SAE paper data collection tool is the preferred method to transmit this information to the Sponsor.
- In rare circumstances and if email transmission is not feasible, notification by telephone is acceptable with a copy of the SAE data collection tool sent by overnight mail or courier service.
- Initial notification via telephone does not replace the need for the Investigator to complete and sign the SAE data collection tool within the designated reporting time frames.
- Contacts for SAE reporting can be found in the Investigator Site File.

